4.1 Overall study design

- This is a phase II randomized study of convalescent plasma for the treatment of non-immune individuals with COVID-19 infection at high risk of complications.

- Subjects will be considered as having completed the study after 2 months (+/- 5) days, unless consent withdrawal or death occurs first.
- Subjects will be randomized to receiving convalescent plasma or best supportive care.
- Patients randomized to best supportive care may receive plasma should they require hospitalization for progression of COVID-19 disease.
- Statistical analysis will be performed as described in the statistical section 8.
- The final analysis will be conducted once the last subject completes the 2-month visit or withdraws from the study.

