7.2 Serious adverse events

7.2.1 Definitions

A SAE is defined as an event that meets at least 1 of the following criteria

- Is fatal or life-threatening
- Requires inpatient hospitalization or prolongation of existing hospitalization, unless hospitalization is a result of:
 1. A routine treatment or monitoring of the studied indication not associated with any deterioration in condition
 2. An elective or preplanned treatment for a pre-existing condition that is unrelated to the indication under study and has not worsened since signing the ICF
 3. A treatment on an emergency outpatient basis for an event not fulfilling any of the definitions of a SAE and not resulting in hospital admission
 4. Any social reasons and respite care, in the absence of any deterioration in the subject's general condition
- Results in persistent or significant disability, incapacity, or a substantial disruption of a person's ability to conduct normal life functions
- Constitutes a congenital anomaly or birth defect
- Is considered to be an important medical event or a medically significant event that may not result in death, be immediately life-threatening, or require hospitalization but may be considered serious when, based upon appropriate medical judgment, the event may jeopardize the subject or may require medical or surgical intervention to prevent 1 of the outcomes listed above.

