7.3 Data Safety Monitoring Board (DSMB)

This study will be approved and monitored by the HackensackUMC DSMB. The DSMB is responsible for the monitoring of investigator initiated research studies to ensure the safety of participants, the integrity of the data, and the appropriate termination of studies in the event that undue risks have been uncovered, or it appears that trials cannot be conducted successfully. The DSMB provides multidisciplinary, independent oversight of research studies conducted by HackensackUMC staff and or affiliates. The DSMB can require protocol modifications related to participant safety and to recommend suspension or termination to the IRB and institutional official of any research protocols that fall within its jurisdiction. The DSMB may request that HackensackUMC's Corporate Compliance Department conduct periodic audits to assure that data are being collected and recorded according to the protocol.

The investigator is required to submit monthly monitoring reports which include current enrollment data, adverse event summary data and any other data requested by the DSMB. The DSMB will meet monthly to review the trial progress, adverse event data, and any relevant information such as significant amendments or reviews from IRB submitted by the principal investigator. If significant concerns are raised by the DSMB, the concerns will be forwarded to the PI as well as recommendations made to the IRB, and Institutional Official. Recommendations may include modifying, suspending, or terminating the protocol.

8. Study Design and Sample Size Considerations

This is a randomized phase II trial to assess the efficacy and safety of treatment with convalescent plasma infusion (Treatment) versus without convalescent plasma infusion (Control) in patients with early COVID-19 infection at high-risk of admission. Eligible subjects will be stratified randomized by their Charlson Comorbidity Index scoring in a 1:1 ratio to receive either Treatment or Control (8.4). For this trial, we have considered a group sequential design which has more interim analyses and utilized a three-stage O'Brien-Fleming design.²³

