8.1 Hypothesis

The primary objective is the hospitalization rate of patients with early COVID-19 infection at high-risk of admission. Suppose the hospitalization rate by 21 days from therapy initiation is 8% for the Treatment group (P_t) and 18% for the Control group (P_c). This phase II design will aim at the following hypothesis:

The design has a type I error rate at 0.05 with statistical power at least 0.80.

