8.2 Study design

This trial will follow a one-sided three-stage O'Brien-Fleming design as follows.²³

The first stage analysis will be after 51 subjects in each arm, that is after a total of 102 subjects. If the Z statistic is greater than or equal to 0.179 (p-value ≥ 0.571), the hypothesis H_0 is accepted and the trial stops, we conclude the Treatment is not worth pursuing; if the Z statistic is less than or equal to -2.849 (p-value ≤ 0.002), the hypothesis H_0 is rejected and early evidence for promising efficacy is established. Otherwise, the trial continues to the next stage.

The second stage analysis will be after 102 subjects in each arm, that is after a total of 204 subjects. If the Z statistic is greater than or equal to -0.944 (p-value ≥ 0.173), the hypothesis H_0 is accepted and the trial stops, we conclude the Treatment is not worth pursuing; and if the Z statistic is less than or equal to -2.015 (p-value ≤ 0.022), the hypothesis H_0 is rejected and early evidence for promising efficacy is established. Otherwise, the trial continues to the final stage.

At the final stage, a total of 306 subjects will be recruit and 153 of them for each arm. The hypothesis H_0 is rejected for efficacy if the Z statistic is less than -1.64504 (p-value < 0.4498). Otherwise, the H_0 is not rejected.

Stage	Cumulative total sample size N	Cumulative sample size for treatment group N(Grp 1)	Cumulative sample size for control group N(Grp 2)	Evidence for undesired rate if Z statistic \geq (Accept H_0 if Z-statistic \geq)	Evidence for desired rate if Z statistic \leq (Reject H_0 if Z-statistic \leq)	Evidence for undesired rate if p-value \geq (Accept H_0 if p-value \geq)	Evidence for desired rate if p-value \leq (Reject H_0 if p-value \leq)
1	102	51	51	0.17929	-2.84929	0.57115	0.00219
2	204	102	102	-0.94399	-2.01475	0.17259	0.02197
3	306	153	153	-1.64504	-1.64504	0.04998	0.04998

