8.3. Analysis Plan

8.3.1 Primary Endpoints

The primary endpoint of the phase II study is the hospitalization rate at 10 days from therapy initiation of patients with early COVID-19 infection at high-risk of admission. The hospitalization rate will be summarized by frequency (%) and compared between the Treatment and Control arms by Mantel-Haenszel test. There will be two interim analyses. Analysis reports will be provided to the DSMB to decide if there is a pronounced treatment effect or futility. A detailed interim analysis plan will be provided before the start of the interim analysis.

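### The detailed interim plan may be written as late as the first look, in a trial with no blinding described and parts of the primary analysis unsettled; it should be locked before outcomes by arm can be seen

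*Combined protocol and SAP*

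**What the plan says.** On the error rate, section 8.1 states: "The design has a type I error rate at 0.05 with statistical power at least 0.80". Section 8.2 says "This trial will follow a one-sided three-stage" O'Brien-Fleming design and tabulates looks at 51, 102 and 153 patients per arm, with efficacy and futility bounds on the Z scale.

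On the interim plan, section 8.3.1 says: "A detailed interim analysis plan will be provided before the start of the interim analysis". No other section sets an earlier date. The interim reports go to the DSMB.

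On the primary analysis, section 8.1 sets the design rates (8% and 18%) at 21 days from therapy initiation, while section 8.3.1 defines the endpoint as the "hospitalization rate at 10 days from therapy initiation". Section 8.3.1 names the Mantel-Haenszel test but not its strata; section 8.4 defines four Charlson groups for the randomization. Section 8 names no analysis set and does not say when therapy initiation occurs for a control patient.

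On who can see what, section 4.1 says: "Subjects will be randomized to receiving convalescent plasma or best supportive care". The protocol summary describes a single-institution study, and neither blinding nor a placebo infusion is mentioned. Section 7.2.1 counts as serious any event that "Requires inpatient hospitalization or prolongation of existing hospitalization", with listed exceptions, and section 7.2.2 has the investigator assess the causal relation of every SAE to treatment. Sections 5.2.2 and 5.2.5 allow control patients to receive plasma once admitted. Section 7.3 adds: "The investigator is required to submit monthly monitoring reports which include current enrollment data, adverse event summary data".

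**The concern.** Group-sequential bounds control the error rate for a statistic chosen without regard to the data. Here the only deadline for the detailed plan falls when 51 patients per arm have been randomized. The primary event, hospital admission, is one the site team meets directly. Judging whether an admission is related to plasma, or deciding whether an admitted control should now receive it, requires knowing the arm. Under the design rates the first look would hold only about 4 against 9 admissions, so a running tally needs no formal analysis.

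If an unsettled element of the primary analysis were decided at that point, the decision could follow the data, even in good faith. That would raise the chance of a false efficacy claim, make a futility stop easier to avoid, and leave a positive result open to challenge.

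**Working it through.** **Step 1: the plan's own figures.** Inputs from section 8.2: efficacy bounds -2.84929, -2.01475, -1.64504; futility bounds 0.17929, -0.94399 at the first two looks; information fractions 1/3, 2/3, 1.
- Shape: -1.64504 × √(3/k) gives -2.84929 (k = 1), -2.01475 (k = 2) and -1.64504 (k = 3), matching the table.
- Type I error by numerical integration, with futility stops followed: 0.00219 + 0.02051 + 0.02730 = 0.0500.
- Power at 8% versus 18% with 153 per arm: 0.802 with unpooled variance, 0.794 with pooled variance.

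The stated 0.05 and roughly 0.80 therefore reproduce. The 0.0500 relies on futility stops being followed; treated as non-binding, the same bounds give 0.0577.

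**Step 2: what can be visible at the first look.** Expected admissions under the design rates are 51 × 0.08 = 4.1 and 51 × 0.18 = 9.2.

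**Step 3: what is unsettled.**
- Window: 21 days (8.1) against 10 days (8.3.1).
- Analysis set: not named. Uninfused Treatment patients are foreseeable. Section 3.2 admits patients up to 96 hours from onset, while section 5.2 allows up to 48 hours from randomization to infusion and still places infusion within 96 hours of onset.
- Statistic: stratified or unstratified Mantel-Haenszel.
- Time zero: therapy initiation is undefined for controls.

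**Step 4: the size if a choice follows the data.** Null simulation with 18% in both arms, 51 per arm per stage and the section 8.2 bounds. The statistic is the pooled Z = (p_t - p_c) / √[p(1 - p)(1/n_t + 1/n_c)], where p is the pooled rate. The version with the smaller Z at look 1 is picked once and then kept. The early-admission and uninfused shares are not in the documents; they are assumptions, shown as ranges.

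| Choice made at look 1 | Assumption | Type I error |
|---|---|---|
| Any one version fixed in advance | none | about 0.050 |
| 10- or 21-day window | 95% of 21-day admissions by day 10 | 0.056 |
| | 90% | 0.059 |
| | 80% | 0.064 |
| | 65% | 0.068 |
| | 50% | 0.071 |
| All randomized or infused only | 5% of Treatment uninfused, at average risk | 0.055 |
| | 10% | 0.056 |
| | 15% | 0.058 |

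Repeat runs differ by up to 0.002. In the same model the null probability of a futility stop at look 1 falls from about 0.45 to 0.37 (80% early) or 0.31 (50% early) when the window is picked. The choice between pooled and unpooled variance matters little: about 0.050 to 0.052.

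**The case against.** The strongest reply is that the core of the design is already prespecified. Looks, sidedness, bounds, a named test and an endpoint are all in section 8, and an independent DSMB receives the interim reports. This stands, and it rules out one tempting inference: that the 0.05 is unprotected as such. It is protected for any single analysis fixed in advance.

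The next reply is that the largest inflation comes from the conflict between 10 and 21 days, not from the late plan. This also largely stands. Correcting one number would remove that component whenever the interim plan is written. The analysis set, strata and time zero would remain open, and of these only the analysis set has been sized, at 0.055 to 0.058. No passage proposes an infused-only primary analysis.

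Third, the figures assume that the favourable version is always picked, so they are ceilings for one binary choice made once. The mild end of the window range is also plausible. Section 1.4 reports that most admitted patients were in their second week of disease, and with infusion within 96 hours of onset, day 10 falls at about symptom day 10 to 14. That suggests, without proving it, that most admissions fall inside 10 days.

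A reader might also infer two things that the documents do not say. One is that the team already knows admissions by arm. They can know, but section 7.3 does not say that the monthly summaries are split by arm, and sections 7.1.1 and 7.1.2 tie adverse events to plasma donation or infusion, so it is unclear that control admissions would appear there. The other is that the endpoint and population have been deferred to the interim plan. Section 8.3.1 promises only a detailed interim plan. These items are simply unsettled, and nothing requires them to be settled earlier.

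DSMB independence does not answer what remains. The documents do not say who writes the plan, or that its author has no access to outcomes by arm.

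**Conclusion.** The point holds as a gap in timing combined with unresolved items, not as a fault in the boundaries. With one analysis fixed beforehand and futility stops followed, type I error is 0.050. If one open choice were made at the first look with outcomes in view, the ceiling is about 0.056 to 0.071 for the window and 0.055 to 0.058 for the analysis set, an excess of roughly 0.005 to 0.021. These figures rest on the assumed shares above and on always choosing the favourable version. They show what could happen; the documents give no evidence that any choice has followed or will follow the data. The combined effect of several open choices was not calculated. The change is worth making because it costs almost nothing and removes a ground for challenging an efficacy claim.

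**What to change.** 1. Reconcile the 21-day window in 8.1 with the 10-day window in 8.3.1. The design rates of 8% and 18% are stated for 21 days, so if the 10-day window is kept they need restating for it.
2. Replace the timing sentence in 8.3.1 with wording to this effect: *The interim analysis plan, including the analysis set, the endpoint window and its time zero in both arms, and the exact stratified Z statistic for all three looks, will be finalized, signed and dated before the first patient is randomized, and will be changed afterwards only by amendment.*
3. If enrolment has begun, have a statistician finalize the plan before any by-arm admission count is tabulated.

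The cost is that the same document is written earlier. No change to the monthly safety report is needed: pooling admissions there would do little when the same team sees each admission, and it would alter what the DSMB receives.

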8.3.2 Safety Assessment

Safety assessment will be performed on infusion days 0 (post infusion), +3 and +7 days by telephone (closest business day is acceptable), +2 weeks (+/- 3 days), +4 weeks (+/- 3 days), 2 months (+/- 5 days). The safety of the trial will be accessed by evaluating the therapies exposure, adverse events (AE), and

death. Adverse events that begin or worsen after initiation of plasma donation or infusion should be recorded on the Adverse Events Form of the CRF.

A summarization of the number of days and/or cycles subjects were exposed to the therapies will be provided. AE (and serious adverse events, SAE) will be graded and recorded throughout the study and during the follow-up period according to the NCI Common Terminology for Adverse Events (CTCAE) v4.03. Toxicities will be characterized in terms regarding seriousness, causality, toxicity grading, and action taken with regard to trial treatment. The percentage of subjects experiencing an adverse event at a given severity, an NCI CTCAE toxicity grade, and the relationship to study therapy, will all be provided. And the number of subject deaths throughout the study will be summarized.

8.3.3 Secondary Endpoints

- Time to Symptoms Resolution

Kaplan-Meier analysis will be used to describe time to symptoms resolution and the median time with 95% CI will be reported. Log-rank test will be utilized to compare the time to symptoms resolution between the Treatment and Control arms.

The time to symptoms resolution is defined as the time in days from therapies initiation to the first documented symptoms resolution as assessed by a local site. Patients whose symptoms are not resolved, or result in death, or lost follow-up on the designed follow-up date, will be censored on that date.

- Overall Survival (OS)

Overall survival (OS) will be defined as the time in days from study entry to death. Patients who are alive on the date of closing follow-up will be censored on that date. All events of death will be included, regardless of whether the event occurred while the subject was still taking new therapies, or after the subject discontinued study therapy. If a subject has not died, then the data will be censored according to the following rule: if the subject was lost to follow-up, then data will be censored at the last study visit, or the last contact date, or the date the subject was last known to be alive, whichever is later. If the subject was not lost to follow-up, then data will be censored at the last study visit or the last contact date, whichever is later.

OS will be estimated by Kaplan-Meier methodology, and median OS with 95% CI will be reported. And the OS between the Treatment and Control arms will be compared by Log-rank test.

- Rate of Virologic Clearance

The rate of virologic clearance by nasopharyngeal swab at 2 weeks and 4 weeks will be summarized by frequency (%) and compared between two randomized arms by Mantel-Haenszel test. The marginal model will be fitted to the rate of virologic clearance at different time points to evaluate the main effect of randomized arms by using the generalized estimating equations method.

Viral clearance at a designed follow-up date is defined as the cycle threshold (Ct) of RT-PCT at that designed follow-up date 40.

- Evaluation of Donor parameters

Donor parameters including nasopharyngeal swab positivity and antibody titer levels. Donor parameters will be summarized by frequency (%) for categorical parameters, and mean (SD) or median [IQR, interquartile range] for continuous parameters based on the data normality. The association between the donor parameters and the hospitalization rate will be checked by Mantel-Haenszel test for categorical donor parameters, and t-test or its non-parametric version for the continuous donor parameters. The logistic regression model will be built to evaluate the main effect of donor parameters on the hospitalization rate.

- Patients' Anti-SARS-CoV2 titer Assessment

Patients' anti-SARS-CoV2 titer will be assessed pre-infusion (for the Treatment group), +2 weeks (+/- 3 days), +4 weeks (+/- 3 days), and +2 months (+/- 5 days). The antibody titers at the designed follow-up date will be summarized by mean (SD) or median [IQR] and compared between the Treatment and Control arms by t-test or its non-parametric version based on the data normality. The mixed-effect linear model will be used to assess the association between antibody titers measures with the randomized arms.

- Baseline Characteristics

All baseline summary statistics and analyses will be based on characteristics prior to the initiation of study drug. Frequency and percentages for categorical variables and mean (SD) or median [IQR] for the continuous variables based on the normalization of the data.

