1.4 Experience at HUMC/JTCC with convalescent plasma in patients with COVID-19

To date 39 patients with COVID-19 hospitalized at HUMC were treated with convalescent plasma under IND 19824. Our review of these patients showed that the treatment is safe with only 1 patient with a plasma infusion-associated rash. Our experience revealed that most patients admitted for COVID-19 were in the second week of their disease and were experiencing immune mediated hypoxemia. 87% of the treated patients were found to have anti-SARS-CoV2 antibody titers prior to the infusion of plasma. This was unexpected at the time of inception of our protocol under IND 19824. The unmet need appears to be in the week preceding admission where patients have unprotected viral infection and tissue invasion. There is precedent of the introduction of antiviral therapy early in the disease process. The oral neuraminidase inhibitor oseltamivir has shown efficacy in reducing duration of symptoms and complication from influenza in patients with less than 36 hours from symptom onset.²¹ We believe that a similar strategy needs to be implemented for convalescent plasma in COVID-19 patients.

2. Study Objectives

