3.2 Patient

- Patient age ≥ 30 years old, newly diagnosed with a COVID-19 infection with onset of first symptoms ≤ 96 hours, and least one other high-risk feature:
 1. Age ≥ 65
 2. BMI 30 or above
 3. Hypertension, defined as SBP above 140 or DBP above 90, or requiring medication for control.
 4. Coronary artery disease (history, not ECG changes only)
 5. Congestive heart failure
 6. Peripheral vascular disease (includes aortic aneurysm ≥ 6 cm)
 7. Cerebrovascular disease (history of CVA or TIA)
 8. Dementia
 9. Chronic pulmonary disease
 10. Liver disease (such as portal hypertension, chronic hepatitis)
 11. Diabetes (excludes diet-controlled alone)
 12. Moderate or severe renal disease defined as having a GFR <60 mL/min
 13. Cancer (exclude if ≥ 5 year in remission)
 14. AIDS (not just HIV positive)

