5.2.2 Plasma infusion day

Patients randomized to the treatment arm will need to be seen on the day of infusion which should occur within 48 hours of randomization and be within 96 hours of symptom onset.

Study plasma administration will be allowed for the Control arm after hospital admission if requested by the patient's medical team.

- On the day of infusion, blood will be drawn for:
 1. Inflammatory markers

- a. D-Dimers
 - b. Ferritin
 - c. CRP
- 2. Serological testing: anti-SARS CoV-2 titers
- 3. Exploratory blood test for genomics (optional)
- 4. Exploratory blood test for cytokines/chemokines (optional)
- 5. Rectal swab for gut microbiome analyses, to be sent to the CDI if possible
- 6. CBC
- 7. Complete chemistry
- 8. ABO Rh

- Procedure:
 - 1. A single unit of approximately 400-500 mL of liquid fresh plasma or 2 units of fresh frozen plasma for a total of approximately 400 mL will be transfused at an approximate rate of 50 mL per hour x 30 minutes, then the rate may be increased up to 150 mL per hour until completion. If plasma availability does not allow for 2 units of FFP, a single unit may be administered.
 - 2. If possible, 10mL of plasma will be collected for research from the infusion line and sent to the CDI
 - 3. The infusion may be slowed or stopped as per investigator's decision for minor transfusion reactions only. The transfusion will be discontinued for any transfusion reactions other than minor allergic reactions.
 - 4. An investigation will be initiated when there are signs of a systemic transfusion reaction.
 - 5. Premedication 30 – 60 minutes prior to the infusion will include 100 mg hydrocortisone IV and may include acetaminophen 650 mg PO and diphenhydramine 25 mg IV. Diphenhydramine 25 mg IV and hydrocortisone 100 mg IV may be repeated as needed for an infusion reaction at the discretion of the investigator.
 - 6. Vitals signs should be monitored following Hackensack Meridian Health Blood and Blood Product Administration SOP guidelines:
 - a. Temperature, pulse, respirations, and blood pressure pre-infusion (within 30 minutes), 15 minutes after the start, every hour during, if a transfusion reaction is suspected or if there is any change in patient condition, post transfusion (5-15 minutes post)

5.2.3 Post enrollment day +3 and day +7 (or closest working day). May be done remotely.

- COVID-19 symptom screen by telephone (Y/N)
 - 1. Fever (T max)
 - 2. Cough
 - 3. Shortness of breath
 - 4. Ageusia and/or anosmia

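### Time to symptoms resolution counts the first clear screen with no durability rule, so a patient who later relapses or is admitted stays an early resolver

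*Combined protocol and SAP*

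**What the plan says.** Section 8.3.3 defines the endpoint as "the time in days from therapies initiation to the first documented symptoms resolution as assessed by a local site". On censoring it says: "Patients whose symptoms are not resolved, or result in death, or lost follow-up on the designed follow-up date, will be censored on that date". On the comparison: "Log-rank test will be utilized to compare the time to symptoms resolution between the Treatment and Control arms". No sentence there or elsewhere deals with symptoms that return, or with an admission after a documented resolution. The section also does not say which screen items must be negative. That all of them must be is the natural reading of the form, not stated text.

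Symptoms are screened as yes/no items by telephone at day +3 and day +7 (5.2.3), then at 2 weeks, 4 weeks and 2 months (5.2.4). There are seven items: fever, cough, shortness of breath, loss of taste or smell, myalgias, headache, and other symptoms the patient attributes to COVID-19. Day 0 is randomization in both arms (5.2).

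Treatment patients are infused within 48 hours of randomization (5.2.2), and premedication "will include 100 mg hydrocortisone IV and may include acetaminophen 650 mg PO". Control has no placebo infusion, and no blinding is described. A Control patient can receive plasma only after admission, by the same procedure (5.2.2, 5.2.5).

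Patients enter within 96 hours of first symptoms, and "Chronic pulmonary disease" and congestive heart failure are among the qualifying features (3.2). Section 1.4 reports that "most patients admitted for COVID-19 were in the second week of their disease".

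**The concern.** The event is fixed by the first clear screen, and nothing that happens later can undo it. In a disease where the sponsor sees admissions mainly in the second week, the two telephone contacts come early. A patient who is briefly clear and then deteriorates enters the Kaplan-Meier curve as one of the fastest recoveries.

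Time to symptoms resolution is the first-listed secondary objective (2.2) and receives a formal test. If short-lived clear screens are equally common in both arms, the curves overstate the speed of recovery in each. If they are not, the comparison itself is distorted.

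Two smaller gaps belong to the same definition. The clock starts at initiation of therapy, which is not defined for Control. Cough and shortness of breath are scored without reference to the patient's state before COVID-19.

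**Working it through.** **1. A worked patient.** Take a patient randomized on day 0, clear on all items at the day +3 call, with symptoms again at day +7 and admitted on day 10. The first documented resolution is the day +3 contact. None of the three censoring conditions applies at that contact, so the patient is an event there. The relapse and the admission have no effect on the endpoint.

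**2. The clock.** A Treatment patient infused on day 2 scores 3 − 2 = 1 day; one infused on day 0 scores 3 − 0 = 3 days. A Control patient has no initiation of therapy. Counted from randomization, the same contact scores 3 days.

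**3. Timing of the early contacts.** Entry is at most 96 hours (4 days) after onset, so the day +3 call falls no later than about 4 + 3 = day 7 of symptoms, and the day +7 call no later than about 4 + 7 = day 11. Infusion falls 0 to 2 days after randomization, so the day +3 call is 1 to 3 days after premedication. The closest-working-day allowance moves these by a day or so.

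**4. Later admissions scored as early resolvers.** The plan gives no power or effect size for this endpoint, so there is no stated figure to reproduce. Section 8.1 gives design admission rates of 8% (Treatment) and 18% (Control); section 8.2 gives 153 per arm.
- Expected admissions: 153 × 0.08 = 12.24 and 153 × 0.18 = 27.54.
- Assume a share q of admitted patients was clear at day +3; the documents give no value. With q = 5%: 0.6 Treatment, 1.4 Control. With q = 30%: 3.7 Treatment, 8.3 Control.
- Excess in Control: (27.54 − 12.24) × q = 15.3q, or 0.8 to 4.6 patients. If the treatment works as designed, this error favours Control.

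**5. Unequal transient clear screens (illustration only).** Lasting resolution was set identical in both arms: 10, 25, 35, 20 and 5% at days 3, 7, 14, 28 and 60, and 5% never. Among patients not yet lastingly resolved, a transient clear screen at day +3 was assumed in 5% of Control and varied in Treatment. There were 153 per arm, a two-sided 0.05 log-rank test and 2,000 simulated trials per row.

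| Treatment vs Control transient rate | Rejects, first-documented rule | Rejects, true lasting date |
|---|---|---|
| 5% vs 5% | 5.1% | 5.3% |
| 10% vs 5% | 8.7% | 4.8% |
| 15% vs 5% | 18.5% | 5.4% |
| 25% vs 5% | 58.0% | 4.9% |

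The last column uses the true lasting date, so it is a benchmark and not a test of a confirmation rule.

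A second model did test confirmation at the next contact. It used exponential resolution with a median of 12 days, 3,000 trials per setting, and a one-sided 2.5% test toward Treatment. With day +3 transient rates of 10, 15 or 20% in Treatment against 5% in Control, the first-documented rule favoured Treatment in 8, 15 or 32% of trials, and the confirmed rule in 2.3 to 3.3%. With equal 5% rates the first-documented rule gave 2.6%. The one-sided 2.5% level is a choice of the illustration: section 8.3.4 sets 0.05 and does not state sidedness.

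**The case against.** The strongest reply is that this is a drafting gap in one secondary endpoint of a phase II trial. Resolving early and being admitted later is not a contradiction, because the endpoints measure different things. Resolution is assessed by the site, which leaves room for judgment. Comorbidity is randomized and stratified by Charlson score (8.4), so chronic cough or breathlessness would cost precision more than it would favour an arm.

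Most of this stands as a limit on size. It does not remove the fault: a site judging the day +3 call cannot know what follows, and the rule then holds that judgment fixed.

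A reader might infer that hydrocortisone biases the endpoint toward Treatment. The documents do not support that. Nothing in them says how long the premedication affects symptoms, and on the natural reading all seven items must be negative, including cough and loss of taste or smell. Acetaminophen is not barred in Control, and an admitted Control patient given plasma receives the same premedication. What is true is narrower: before the first call, protocol-mandated hydrocortisone goes to Treatment outpatients only.

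A reader might also infer from section 1.4 that a quiet interval often precedes deterioration. That section describes patients already admitted and says nothing about symptom-free intervals beforehand.

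**Conclusion.** The point holds as a fault of classification. By its stated rule, the plan scores a patient who is clear at day +3 and later relapses or is admitted for COVID-19 as an early resolver. This follows from the text alone, given the natural reading of a clear screen.

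A difference between arms is possible but not shown. Later admissions would flatter Control at the design rates, by 0.8 to 4.6 patients on the assumed shares. A transient premedication effect would flatter Treatment. The net direction is not fixed.

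The simulated rejection rates should not be read as this trial's error rate. All the inflation comes from the assumed gap between arms: equal transient rates keep the nominal level, and the large figures need a gap of three-fold or more that has no source in the documents. Nor should it be inferred that patients with chronic lung or heart disease can never screen clear; the plan is silent on how their usual symptoms are scored.

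This is a cheap improvement to a secondary endpoint. The primary analysis is untouched.

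**What to change.** In 8.3.3, before any outcome data are compared:
- Define the event as all listed COVID-19 symptoms absent, or back to the patient's pre-COVID level, at a scheduled contact and still so at the next attended scheduled contact. Date it at the first of the two.
- Accept a first clear screen at the 2-month visit, since no later contact exists. State how an earlier clear screen with no later attended contact is handled.
- Count a patient with a COVID-19 admission or death after an apparent resolution as not resolved at that earlier contact. Treat death as a competing event, or censor it at the end of follow-up. This clause is needed because confirmation alone would still pass a patient who is clear at days +3 and +7 and admitted in days 8 to 14.
- Count time from randomization in both arms.

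At the day 0 screen (5.2.1), record for each symptom whether it was present before COVID-19.

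The cost is SAP wording and one CRF column. There are no new visits and no change to care. The downside is slightly fewer and later events, and an incidental symptom at a widely spaced later contact may delay some resolutions. The full rule, with the admission clause, has not been simulated.
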